**PASS Information**

Title	Pregnancy outcomes in Multiple Sclerosis populations exposed and unexposed to interferon $\beta$ – a register-based study in the Nordic countries
Protocol version identifier	ER-9430
Date of last version of protocol	18 August 2015
EU PAS register number	Study not yet registered, to be registered.
Active substances	Interferon (IFN)- $\beta$ -1a (L03AB07) IFN- $\beta$ -1b (L03AB08)
Medicinal products	Avonex, Betaferon, Extavia, Plegridy, Rebif
Procedure number	Avonex: EMEA/H/C/000102 Betaferon: EMEA/H/C/000081 Extavia: EMEA/H/C/000933 Plegridy: EMEA/H/C/002827 Rebif: EMEA/H/C/000136
Marketing authorization holder(s) (MAH)s	Avonex, Plegridy: Biogen Idec Ltd Betaferon: Bayer Pharma AG Extavia: Novartis Pharma AG Rebif: Merck Serono Europe Ltd
Joint PASS	Yes
Research question and objectives	The overall research question of this study is to determine if exposure to IFN- $\beta$ s before or during pregnancy has an adverse effect on pregnancy outcomes in patients with Multiple Sclerosis (MS) including, as requested by the Committee for the Medicinal Products for Human Use (CHMP), the identification of the prevalence of adverse pregnancy outcomes in women with MS unexposed to IFN- $\beta$ products.
Countries of the study	Finland (FIN) Norway (NOR) Sweden (SWE)
Author	[name], EPID Research, [name] Email: [contact] [contact]

## 1 List of abbreviations

### List of main abbreviations used in the study protocol

AGA	Average for Gestational Age
ATC	Anatomical Therapeutic Chemical
BMI	Body Mass Index
CHMP	Committee for Medicinal Products for Human Use
CI	Confidence Interval
CS	Caesarean Section
DDD	Defined Daily Dose
DPP	Drugs and Pregnancy Project
ENCePP	European Network of Centres for Pharmacoepidemiology and Pharmacovigilance
EUROCAT	European Surveillance of Congenital Anomalies
FIN	Finland
GW	Gestational Week
ICD	International Classification of Diseases
IFN- $\beta$	Interferon beta
LBW	Low Birth Weight
LBH	Low Birth Height
LGA	Large for Gestational Age
LMP	Last Menstrual Period
MAH	Marketing Authorisation Holder
MBR	Medical Birth Register
MCA	Major Congenital Anomaly
MS	Multiple Sclerosis
MSDMD	MS Disease Modifying Drug
NIPH	Norwegian Institute of Public Health
NCSP	NOMESCO classification of surgical procedures
NOR	Norway
PIN	Personal Identification Number
RR	Relative Risk
SD	Standard Deviation
SF	Statistics Finland
SGA	Small for Gestational Age
SID	Study Identification Number
SII	Social Insurance Institution
SWE	Sweden

THL	Finnish National Institute for Health and Welfare
TOPFA	Termination Of Pregnancy due to Foetal Anomaly
Valvira	National Supervisory Authority for Welfare and Health

## 2 Terminology

**Birth** A process resulting in a foetus or a child (one or more,  $\geq 1$ ) of at least 22+0 gestational weeks (GW) ( $\geq 22+0$  GW) or weighing at least 500 grams ( $\geq 500$  g) being born by vaginal delivery or by caesarean section (CS). The process of a child being born alive is always a birth.

**Birth weight adjusted for gestational age** is defined according to the gestational age and sex-specific national standards in each country (FIN: Sankilampi et al. 2013). Average for Gestational Age (AGA) is used as reference outcome in relation to Small for Gestational Age (SGA) and Large for Gestational Age (LGA).

**Defect cases:** Cases where 3 or more minor anomalies were detected in the same child.

**Gestational age at birth** is a measure of the age of a pregnancy at birth where the origin is the first day of the woman's last normal menstrual period. Preterm birth refers to gestational age less than 37 GW.

**Induced abortion / elective termination of pregnancy** is artificially induced termination of pregnancy which does not comply with the definition of a birth and which leads to the death of one or more foetus ( $\geq 1$ ) and in which there is no indication of intrauterine foetal death before the termination.

**Live birth** is birth of a child that, irrespective of the duration of the pregnancy, breathes or shows any other evidence of life, such as beating of the heart, pulsation of the umbilical cord or movement of the voluntary muscles, whether or not the placenta is attached or the umbilical cord has been cut.

**Major congenital anomaly (MCA)** refers to a major congenital / foetal structural anomaly, chromosomal defect, teratoma and congenital hypothyroidism involved in a birth, an elective termination of pregnancy for severe MCA, or in a spontaneous abortion. MCAs do not include hereditary diseases and other diseases not associated with congenital anomalies, dysfunction of organs or tissues, developmental disabilities, congenital infections, isolated minor dysmorphic features, normal variations and common less significant congenital anomalies.

**Pregnancy event** refers to terminations of pregnancy, spontaneous abortions, ectopic pregnancies, stillbirths and live births.

**Serious adverse pregnancy outcome** is defined as a composite endpoint of pregnancy including elective termination of pregnancy due to foetal anomaly (TOPFA), MCA or stillbirth.

**Spontaneous abortion / miscarriage** refers to spontaneous loss of a pregnancy which does not comply with the definition of a birth or a spontaneous intrauterine death of a foetus, detected by a reliable prenatal diagnostic method, and the associated artificial expulsion of the foetus concerned before 22+0 GW ( $< 22+0$  GW), when the foetus weighs less than 500 grams ( $< 500$  g) according to the International Classification of Diseases, 10th revision (ICD-10) diagnosis O03 (WHO, 2014).

**Stillbirth** is birth of a foetus or a child that shows no evidence of life, but complying with the definition of a birth (22+0 GW or  $\geq 500$  g).

**Pregnancy trimesters** are divided as follows: 1st trimester 0-12 GW, 0-84 days from last menstrual period (LMP), 2nd trimester 13-26 GW, 85-182 days from LMP, 3rd trimester from 27 GW to delivery (approximately 40-42 GW), 183 days from LMP to delivery (approximately 280 days).

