- Information will be obtained from the DPP (FIN) and MBR (SWE, NOR). The Finnish DPP and Norwegian MBR include information on all stillbirths of fetuses with a birth weight of at least 500 g or with a gestational age of at least 22+0 GW. The Swedish MBR includes data on stillbirths after 28 GW.

Live Birth (P):

- Information on live births will be obtained from the DPP (FIN) and MBR (SWE, NOR)

MCAs (P):

- Information will be obtained from the DPP (FIN), Patient Register (SWE) and MBR (SWE, NOR). The study will concentrate on MCAs. These outcomes are registered according to ICD-9 classification into 25 groups (ICD-codes 740-759). Minor anomalies will principally be excluded according to the European Surveillance of Congenital Anomalies (EUROCAT).

Defect cases (E):

- Information will be obtained from the DPP (FIN), Patient Register (SWE) and MBR (SWE, NOR). Defect cases with 3 or more minor anomalies will be defined according to the European Surveillance of Congenital Anomalies (EUROCAT).

Serious adverse pregnancy outcome (P):

- A composite endpoint including presence of elective TOPFA, MCA or stillbirth.

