### 9.7.6 Sensitivity analyses

- Lack of information on terminations of pregnancy due to foetal anomalies from SWE may yield underestimation of the prevalence of MCA in the study population. In FIN, 10.5% of total cases with MCAs were diagnosed and recorded in TOPFAs between 1993 and 2010. However, this may bias the study results on MCAs if the risk for TOPFA differs between women with different MSDMD exposures or MS exposure in SWE. Separate analyses will be performed on MCAs for the Norwegian and the Finnish data including pregnancy terminations, stillbirths and live births, and another analysis including live births only. The analyses will also be stratified by country as the follow-up times of the newborn babies for recording the malformations in MBRs or Malformation Register may vary between the countries.

- Information on pregnancy terminations is available from GW 12 onwards from the Norwegian data, and therefore, information on early pregnancy terminations conducted before GW 12 could result in incomplete data. Therefore separate analyses by trimesters on pregnancy terminations will be performed.
- In additional sensitivity analyses on MCAs, outcomes will be assessed where exposure occurred prior to pregnancy and through to the end of the first trimester of pregnancy. Also, an analysis of MCA outcomes from live births only will be performed.
- As there is a geographical variation in MS prevalence not only between countries but also within countries, descriptive statistics will be conducted by country and university hospital district level. Country and region will also be included in the multivariate analyses.
- Possible changes in diagnostic criteria and developments in examination and treatment throughout time, as well as trends in obstetric care may influence the estimated prevalence. The study periods also vary between the countries, which may reflect the deviation in the results. Therefore the year of pregnancy outcome will be taken into account in the descriptive statistics and analyses. By taking into account the data from 1 Jan 2005 to 31 Dec 2014 from each country (time period in which the data is available i.e. overlaps for all 3 countries), a separate sensitivity analysis of the primary objective will be provided as well.

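### MCA, and with it the primary composite, counts chromosomal defects, and no analysis listed in the protocol separates them, so an effect on other anomalies is diluted towards RR 1

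*Protocol*

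**What the plan says.** Protocol section 2 (Terminology) states that MCA "refers to a major congenital / foetal structural anomaly, chromosomal defect, teratoma and congenital hypothyroidism involved in a birth", and extends the term to terminations for severe MCA and to spontaneous abortions. The exclusions that follow ("MCAs do not include hereditary diseases and other diseases not associated with congenital anomalies, dysfunction of organs or tissues", then developmental disability, infections, and minor or common less significant features) do not take chromosomal defects out.

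Section 9.4 keeps the whole anomaly range: "These outcomes are registered according to ICD-9 classification into 25 groups (ICD-codes 740-759"). Its only stated removal is that "Minor anomalies will principally be excluded according to the European Surveillance of Congenital Anomalies (EUROCAT"). The 25 groups describe how cases are registered, and no analysis by group is announced. The primary outcome is "A composite endpoint including presence of elective TOPFA, MCA or stillbirth", so MCA and TOPFA enter it whole. MCA is also compared in its own right under objective 2 (cohorts 1 vs 3 and 1 vs 4).

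The MCA sensitivity analyses in 9.7.6 change three things:

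- **Countries and birth types:** "Separate analyses will be performed on MCAs for the Norwegian and the Finnish data including pregnancy terminations, stillbirths and live births", plus an analysis of live births only.
- **Stratification:** by country, because malformation follow-up differs.
- **Exposure window:** "outcomes will be assessed where exposure occurred prior to pregnancy and through to the end of the first trimester of pregnancy".

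Section 9.9 repeats the country and birth-type variants. Chromosomal defects are not mentioned as outcomes after section 2.

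**The concern.** The study asks whether IFN-β before or during pregnancy harms the pregnancy. An effect on foetal development would appear in structural anomalies and in terminations or stillbirths that follow from them. A chromosomal defect is set at or about conception, so exposure after that point cannot produce it. Counting such defects adds about the same number of unresponsive events per pregnancy to both cohorts and moves the RR towards 1. In a safety study that is the reassuring direction.

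The first-trimester analysis shows the gap most clearly. It narrows exposure to the period relevant to malformation, yet still counts anomalies fixed before most of that period. As listed, the analyses cannot tell a weak effect on all events from a stronger effect on the non-chromosomal ones.

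**Working it through.** **Inputs from the protocol (9.5).** Cohort 1 n1 = 294; cohort 3 n0 = 1270; baseline composite prevalence p0 = 7.3% (24/331 = 7.25%); two-sided 5% level; 80% power; minimum detectable RR 1.72.

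**Input not in the protocol.** f is the share of baseline composite events that are chromosomal. It is assumed to be 5, 10, 15 or 20%.

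**Step 1: reproduce the stated figure.** The two-proportion normal approximation with pooled null variance and no continuity correction is

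power = Φ[(p1 − p0 − 1.96·s0)/s1]

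where s0 = √[p̄(1 − p̄)(1/n1 + 1/n0)], s1 = √[p1(1 − p1)/n1 + p0(1 − p0)/n0], and p̄ is the pooled proportion.

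At RR 1.72:

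- p1 = 0.073 × 1.72 = 0.12556, p̄ = 0.08288, s0 = 0.01784, s1 = 0.02066
- (0.05256 − 1.96 × 0.01784)/0.02066 = 0.851, so power = 0.803

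Solving for 80% power gives RR 1.717 at 7.3% and 1.720 at 24/331, which matches the stated 1.72. At baselines of 6, 5, 4 and 3% the same formula gives 1.81, 1.90, 2.03 and 2.23. The protocol states 1.81, 1.91, 2.04 and 2.23.

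**Step 2: dilution.** If f·p0 does not respond to exposure and (1 − f)·p0 is multiplied by the true RR, prevalence in the exposed is p0[f + (1 − f)RR]. Hence

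observed RR = 1 + (1 − f)(RR − 1)

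For RR = 1.72 and f = 20%: 1 + 0.80 × 0.72 = 1.576.

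**Step 3: power with and without these events.** Counted: baseline 7.3% with the observed RR. Not counted: baseline 7.3% × (1 − f) with RR 1.72. Denominators are unchanged.

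| Assumed f | Observed RR | Power, counted | Baseline, not counted | Power, not counted | Gain (points) |
|---|---|---|---|---|---|
| 5% | 1.68 | 77% | 6.94% | 78% | 1 |
| 10% | 1.65 | 73% | 6.57% | 76% | 3 |
| 15% | 1.61 | 69% | 6.21% | 74% | 5 |
| 20% | 1.58 | 65% | 5.84% | 71% | 7 |

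**Step 4: scale in events.** Cohort 1 expects 294 × 0.073 = 21.5 background events. Shares of 5 to 20% are therefore about 1 to 4 of them.

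**Step 5: MCA alone.** All chromosomal cases lie inside MCA, while the composite also holds stillbirths that may carry no anomaly. Where such stillbirths occur, f is larger for MCA than for the composite and the dilution is stronger. Section 9.9 already says the study is not powered for individual outcomes.

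**The case against.** Five points can be made for the plan.

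**The exposure is not only post-conception.** Section 9.4 counts purchases up to six months before the last menstrual period, and some cohort 1 women may have had pre-conception exposure only. A reader might infer that no exposure studied here could bear on chromosomal events. The protocol does not support that, because timing rules out a cause only for exposure after conception. This point stands, and it is why the all-MCA composite should be kept.

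**Age is handled.** A reader might infer that chromosomal cases bring in uncontrolled age confounding. Section 9.7.3 puts maternal age at the last menstrual period in the base model, and objective 5 stratifies by it. At most residual confounding remains. Age adjustment does not remove dilution, however, which arises even when the cohorts have the same ages.

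**The stated power is not wrong.** The figure of 1.72 is for the composite as defined, with a baseline taken from that same composite, and it reproduces. An all-MCA count also serves the regulator's request for background prevalence. Both stand.

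**The gain is modest.** A reader might take the fall from 80% to as low as 65% as what the remedy recovers. Removing these events also lowers the event count, so the recovery is 1 to 7 points. This stands.

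**The separate analysis plan may cover it.** Section 9.7 defers detail to that plan, which is not available here, so the gap can be asserted only of the protocol. The protocol does, however, fix the MCA definition and itemise the MCA sensitivity analyses itself, and this split is not among them.

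**Conclusion.** The point holds as a gap in the listed sensitivity analyses, not as an error in the primary analysis. Chromosomal defects count as MCA, feed the composite by two routes, and are separated nowhere in the protocol. For any non-zero share, a true RR above 1 on the remaining events is understated.

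The size is uncertain. At an assumed 5% the change from 1.72 to 1.68 is negligible beside the 1.72 to 2.23 range that section 9.5 already shows. At 20%, an observed 1.58 with 65% power is material. The figures assume that chromosomal events are unaffected by exposure, that f refers to the unexposed baseline, and that the crude two-proportion approximation stands in for the adjusted model.

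The documents do not support calling the composite invalid or replacing it as primary. This is a low-cost improvement.

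**What to change.** Keep the composite as the primary outcome. In 9.7.6 add a sensitivity analysis of MCA and of the composite, for cohorts 1 vs 3 and 1 vs 4, in which isolated chromosomal defects are not counted as events. TOPFA for such defects should also not count where the anomaly code is available (Finland and Norway; Sweden has no termination data). These pregnancies stay in the denominator. Define in advance what isolated means, and whether a stillbirth with such a defect still counts as a stillbirth. Under objective 1, report chromosomal and non-chromosomal MCA as separate rows, so that a pre-conception signal would remain visible.

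The cost is a code filter and one further table on anomaly data already requested. The downsides are fewer events in that analysis and its dependence on anomaly codes for terminations, which the protocol does not confirm will be supplied. Specifying it before the data are seen avoids a post hoc choice of which anomalies to count.

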### 4 Abstract

Version 2.0, 18 August 2015, [name], Adjunct Professor of Biostatistics, EPID Research Oy

#### **Pregnancy outcomes in Multiple Sclerosis populations exposed and unexposed to interferon $\beta$ – a register-based study in the Nordic countries**

**Rationale and background:** MS is the most common chronic neurologic disability in young adult females in their childbearing ages. Little evidence is available regarding the association between exposure to IFN- $\beta$  products and adverse pregnancy outcomes. Therefore the four marketing holders of IFN- $\beta$  are conducting a European-wide IFN- $\beta$  pregnancy registry. Additionally, the CHMP has requested a study to enable identification of pregnancy outcomes in the MS population unexposed to IFN- $\beta$  products for comparison with the ongoing European IFN- $\beta$  Pregnancy Registry.

**Research question and objectives:** The overall research question of this study is to determine if exposure to IFN- $\beta$ s before or during pregnancy has an adverse effect on pregnancy outcomes in patients with MS including, as requested by the CHMP, the identification of the prevalence of adverse pregnancy outcomes in women with MS unexposed to IFN- $\beta$  products. The primary objectives are to compare the prevalence of the serious adverse pregnancy outcomes between women with MS exposed to IFN- $\beta$  only vs. unexposed to any MS disease modifying drugs (MSDMDs) and women with MS exposed to IFN- $\beta$  only vs. unexposed to IFN- $\beta$  regardless of exposure to other MSDMDs. The cohorts from this study will provide background prevalence estimates for pregnancy outcomes in MS for the European IFN- $\beta$  Pregnancy Registry. However, the estimated prevalence from this study will not be directly compared with those from the European IFN- $\beta$  Pregnancy Registry.

Comparison of pregnancy outcomes will be conducted by exposure status to IFN- $\beta$ s before and during pregnancy (exposed vs. unexposed) and other MSDMDs.

**Study design:** The present study is a population-based cohort study based on register data from three Nordic countries: FIN, SWE and NOR.

**Population:** The target study population consists of Finnish, Swedish and Norwegian women diagnosed with MS who have been pregnant during the study period from 1996 to 2014. The pregnancy may have resulted in an induced abortion, spontaneous abortion, ectopic pregnancy, stillbirth, or live birth during the study period. A pregnancy will be considered unexposed if exposure is stopped at least three months prior to LMP (exceptions: six months for mitoxantrone and cladribine). MSDMDs that will be considered aside from IFN  $\beta$ -1a, IFN  $\beta$ -1b and Peg IFN- $\beta$ -1-a: human normal immunoglobulin (Anatomical Therapeutic Chemical (ATC) code, J06BA02), cyclophosphamide (L01AA01), methotrexate (L01BA01, L04AX03), cladribine (L01BB04), mitoxantrone (L01DB07), alemtuzumab (L01XC04), glatiramer acetate (Copaxone®) (L03AX13), leflunomide (L04AA13), natalizumab (L04AA23), fingolimod (L04AA27), teriflunomide (L04AA31), azathioprine (L04AX01), dimethyl fumarate (N07XX09).

**Comparisons:** The primary comparisons will be performed between the following study cohorts:

- i) women with MS exposed to IFN- $\beta$  (but not to other MSDMDs) (cohort 1) and women with MS unexposed to any MSDMDs (cohort 3), and,
- ii) women with MS exposed to IFN- $\beta$  (but not to other MSDMDs) (cohort 1) and women with MS unexposed to IFN- $\beta$  regardless of exposure to other MSDMDs (cohort 4).

**Outcomes:** The primary outcome variable is a serious adverse pregnancy outcome, which is defined as a composite endpoint including elective TOPFA, MCA, or stillbirth. Other outcome variables include live births, stillbirths, elective TOPFA or elective termination due to other reasons, MCA, spontaneous abortions, ectopic pregnancies, and several other perinatal adverse health outcomes.

**Data sources:** The study database will be constructed from the Nordic health registers: Drugs and pregnancy Project (DPP) (FIN), Patient Registers, MS Registers, Prescription Registers, Medical Birth Registers (MBRs), Malformation Register, Causes of Death Register, and Population Registers.

**Study size:** The estimated number of pregnancies in MS patients is 1671, encompassing data from:

- i) FIN: 1 January 1996 – 31 December 2014;
- ii) SWE: 1 July 2005 – 31 December 2014;
- iii) NOR: 1 January 2004 – 31 December 2014.

Of these pregnancies, 76% (n=1270) are estimated to be unexposed to any MSDMDs, 22% (n=368) exposed to IFN- $\beta$  regardless of exposure to other MSDMDs, and 18% (n=294) exposed to IFN- $\beta$  only. With an anticipated background rate of 7.3% for the serious adverse pregnancy outcome, the minimum detectable effect size between the study cohorts of MS women exposed to IFN- $\beta$  only vs. MS women unexposed to any MSDMDs is 1.72 in terms of relative risk (RR) with an 80% power and 5% significance level.

**Data analysis:** The individual patient-level data from each country will be pooled into a single dataset and analyses will be conducted using the pooled dataset. The study cohorts will be characterised by country of residence, university hospital district, maternal age at LMP, year of pregnancy outcome, pre-pregnancy weight, pre-pregnancy body mass index (BMI), number of previous pregnancies, number of previous abortions, smoking status during pregnancy, number of foetuses in pregnancy (single vs. multiple), any chronic diseases, exposure to any teratogenic medications including steroids, time since MS diagnosis, and duration of MS treatment. These variables are also used as potential confounders when comparing the pregnancy outcomes between the study cohorts.

The descriptive statistics including number of events (n) and prevalence (%) will be presented for each pregnancy outcome in each study cohort separately. Descriptive analyses of the pregnancy outcomes within each study cohort will be further stratified by country, year of pregnancy outcome, maternal age at LMP, any chronic diseases, exposure to any teratogenic medication including steroids, time since MS diagnosis, duration of MS treatment, gestational age, and weight of the newborn as relevant for specific pregnancy outcomes.

The prevalence of the pregnancy outcomes will be further compared between the study cohorts using log-binomial regression with adjustments for i) baseline potential confounders (country, year, maternal age at LMP, previous pregnancies, chronic diseases, exposure to teratogenic medications including steroids) and ii) all relevant confounders. The RR estimates with 95% confidence intervals (CI) and associated p-values will be reported for these comparisons and for confounders used in the model. Confounding factors will be taken into account in the analyses according to availability and available time period from each register source.

Analyses of congenital malformations, ectopic pregnancies, spontaneous abortions, live births and stillbirths in the general population of women without MS in FIN, SWE and NOR will be based on relevant official birth health statistics available from these countries. The expected numbers of these outcomes in each study cohort will be estimated based on the age-matched population prevalence in each country and compared with the observed number of events using standardized prevalence ratios with 95% CIs.

